8.3.3 NON-TARGET LESIONS

Any other measurable and abnormal nodal lesions not selected for quantitation as target lesions may be considered non-target lesions. In addition, non-measurable evidence of CLL such as nodal lesions with both diameters <1.0 cm, extra-nodal lesions, bone lesions, leptomeningeal disease, ascites, pleural or pericardial effusions, lymphangitis of the skin or lung, abdominal masses that are not confirmed and followed by imaging techniques, cystic lesions, previously irradiated lesions, and lesions with artifacts may be considered as non-target disease.

The presence or absence of non-target disease should be recorded at baseline and as per the study assessment schedule. If present at baseline, up to 6 non-target lesions should be recorded. The non-target disease at baseline will be used as a general reference to further characterize regression or progression of CLL during assessments of the objective tumor response during treatment. Measurements are not required and these lesions should be followed as "present" or "absent".

8.4 DEFINITIONS OF TUMOR RESPONSE AND PROGRESSION

Responses will be categorized as CR, PR, PR-L, SD, or PD. In addition, a response category of not evaluable (NE) is provided for situations in which there is inadequate information to otherwise categorize response status.

The best overall response will be determined. The best overall response is the best response recorded from the start of treatment until disease/recurrence progression (taking as a reference for disease progression the smallest measurements recorded since treatment started). Where imaging data are available, these data will supersede physical examination data in determining tumor status.

8.5 COMPLETE RESPONSE

To satisfy criteria for a CR, all of the following criteria must be met:

TGR-1202-201-CLL

- No evidence of new disease
- ALC in peripheral blood of <4 x 109/L
- Regression of all target nodal masses to normal size ≤1.5 cm in the LD (if applicable)
- Normal spleen and liver size
- Regression to normal of all nodal non-target disease and disappearance of all detectable nonnodal, non-target disease
- Morphologically negative bone marrow defined as <30% of nucleated cells being lymphoid cells and no lymphoid nodules in a bone marrow sample that is normocellular for age
- · Peripheral blood counts meeting all of the following criteria:
 - ANC >1.5 x 10⁹/L without need for exogenous growth factors (e.g., G-CSF)
 - Platelet count ≥100 x 109/L without need for exogenous growth factors
 - Hemoglobin ≥110 g/L (11.0 g/dL) without red blood cell transfusions or need for exogenous growth factors (e.g., erythropoietin)

Subjects who fulfill all the criteria for a CR (including bone marrow criteria) but who have a persistent anemia, thrombocytopenia, or neutropenia or a hypo cellular bone marrow related to prior or ongoing drug toxicity (not to CLL) will be considered as a CR with incomplete marrow recovery (CRi).

8.6 PARTIAL RESPONSE

To satisfy criteria for a PR, all of the following criteria must be met:

- No evidence of new disease
- A change in disease status meeting ≥2 of the following criteria, with 2 exceptions in which
 only 1 criterion is needed: 1) only lymphadenopathy is present at baseline; 2) only
 lymphadenopathy and lymphocytosis are present at baseline. In these 2 cases, only
 lymphadenopathy must improve to the extent specified below:
 - In a subject with baseline lymphocytosis (ALC ≥4 x 10⁹/L), a decrease in peripheral blood ALC by ≥50% from baseline or a decrease to <4 x 10⁹/L
 - A decrease by ≥50% from the baseline in the SPD of the target nodal lesions (if applicable)
 - In a subject with enlargement of the spleen at baseline, a splenomegaly response as defined in Section 8.3.2
 - In a subject with enlargement of the liver at baseline, a hepatomegaly response as defined in Section 8.3.2
 - A decrease by ≥50% from baseline in the CLL marrow infiltrate or in B-lymphoid nodules
- No target, splenic, liver, or non-target disease with worsening that meets the criteria for definitive PD
- Peripheral blood counts meeting 1 of the following criteria:
 - ANC >1.5 x 10⁹/L or >50% increase over baseline without need for exogenous growth factors (e.g., G-CSF)
 - Platelet count ≥100 x 10⁹/L or ≥50% increase over baseline without need for exogenous growth factors
 - Hemoglobin ≥110 g/L (11.0 g/dL) or ≥50% increase over baseline without red blood cell transfusions or need for exogenous growth factors (e.g., erythropoietin)

The proportion of subjects who achieve a PR with lymphocytosis will be recorded.⁷

TGR-1202-201-CLL

To satisfy criteria for SD, the following criteria must be met:

- No evidence of new disease
- There is neither sufficient evidence of tumor shrinkage to qualify for PR nor sufficient evidence of tumor growth to qualify for definitive PD

8.8 DEFINITIVE DISEASE PROGRESSION

The occurrence of any of the following events indicates definitive PD:

- Evidence of any new disease
- A new node that measures >1.5 cm in the LD and >1.0 cm in the LPD
- New or recurrent splenomegaly, with a minimum LVD of 14 cm
- New or recurrent hepatomegaly, with a minimum LVD of 20 cm
- Unequivocal reappearance of an extra-nodal lesion that had resolved
- A new unequivocal extra-nodal lesion of any size
- *New non-target disease (e.g., effusions, ascites, or other organ abnormalities related to CLL).

*Isolated new effusions, ascites, or other organ abnormalities are not sufficient evidence alone of PD unless histologically confirmed. Thus, a declaration of PD should not be made if this is the only manifestation of apparently new disease.

- Evidence of worsening of target lesions, spleen or liver, or non-target disease:
 - Increase from the nadir by ≥50% from the nadir in the SPD of target lesions (if applicable)
 - Increase from the nadir by ≥50% in the LD of an individual node or extra-nodal mass that now has an LD of >1.5 cm and an LPD of > 1.0 cm (if applicable)
 - Splenic progression, defined as an increase in splenic enlargement by ≥50% from nadir (with a minimum 2 cm increase and a minimum LVD of 14 cm)
 - Hepatic progression, defined as an increase in hepatic enlargement by ≥50% from nadir (with a minimum 2 cm increase and minimum LVD of 20 cm)
 - Unequivocal increase in the size of non-target disease (e.g., effusions, ascites, or other organ abnormalities related to CLL)
 - Transformation to a more aggressive histology (e.g., Richter's syndrome) as established by biopsy (with the date of the biopsy being considered the date of CLL progression if the subject has no earlier objective documentation of CLL progression).
- Decrease in platelet count or hemoglobin that is attributable to CLL, is not attributable to an autoimmune phenomenon, and is confirmed by bone marrow biopsy showing an infiltrate of clonal CLL cells
 - \circ The current platelet count is <100 x 10 9 /L and there has been a decrease by >50% from the highest on-study platelet count
 - o The current hemoglobin is <110 g/L (11.0 g/dL) and there has been a decrease by >20 g/L (2 g/dL) from the highest on-study hemoglobin

If there is uncertainty regarding whether there is true progression, the subject should continue study treatment and remain under close observation pending confirmation of progression status by the study chair. In particular, worsening of constitutional symptoms in the absence of objective evidence

of worsening CLL will not be considered definitive disease progression; in such subjects, both CLL-related and non-CLL-related causes for the constitutional symptoms should be considered.

Worsening of disease during temporary interruption of study treatment (e.g., for intercurrent illness) is not necessarily indicative of resistance to study treatment. In these instances, CT/MRI or other relevant evaluations should be considered in order to document whether definitive disease progression has occurred. If subsequent evaluations suggest that the subject has experienced persistent definitive CLL progression, then the date of progression should be the time point at which progression was first objectively documented.

8.9 NON-EVALUABLE

In a subject who does not have evidence of PD, the occurrence of any of the following conditions indicates a response status of NE:

- There are no images or inadequate or missing images
- Images of the liver and spleen are missing at that time point (with the exception that absence
 of splenic images will not result in an NE designation in a subject known to have undergone
 splenectomy).

A time point will be considered to have a response of NE if any target lesion is missing. PD may be assigned at any time point regardless of the extent of missing target or non-target lesions. Missing non-target lesions will not impact the ability to assess for response or disease progression.

8.10 LYMPHOCYTOSIS DURING THERAPY

Upon initiation of umbralisib, a temporary increase in lymphocyte counts (i.e., $\geq 50\%$ increase from baseline and above absolute lymphocyte count of 5,000/mcL) may occur. The onset of isolated lymphocytosis usually occurs during the first few weeks of umbralisib therapy and usually resolves within three to four months. Subjects with lymphocytosis should be continued on study drug until the occurrence of definitive disease progression (i.e., disease progression that is manifest by worsening CLL-related signs other than lymphocytosis alone), or the occurrence of another reason to discontinue study therapy.⁷

9 STATISTICAL CONSIDERATIONS

9.1 SAMPLE SIZE

9.2 GENERAL ANALYSIS CONVENTION

Unless otherwise stated, all analyses will be performed using SAS Version 9.2 or higher and all hypothesis tests will be conducted at a two-sided significance level of 0.05.

In general, summary tabulations will display the number of observations, mean, standard deviation, median, minimum, maximum, and appropriate percentiles for continuous variables, and the number and percentage by category for categorical data. Summaries will be presented. The data listings will include all available efficacy and safety data.

9.3 STUDY POPULATIONS

Two study populations, intent-to-treat (ITT) and safety populations, are pre-defined for this study. The ITT population will include all enrolled subjects who provide some efficacy assessments and the safety population will include all subjects who take at least one dose of study medication. The efficacy analyses will be based on ITT population and the safety analyses will be based on the safety population.

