- 3. Treatment with prior umbralisib.
- Prior autologous stem cell transplant within 3 months. Prior allogeneic hematologic stem cell transplant within 1 year and excluded if there is active graft versus host disease.
- 5. Anaphylaxis to prior kinase inhibitor therapy.
- 6. Evidence of chronic active Hepatitis B (HBV, not including patients with prior hepatitis B vaccination; or positive serum Hepatitis B antibody) or chronic active Hepatitis C infection (HCV), cytomegalovirus (CMV), or known history of HIV. If HBc antibody, HCV antibody or CMV is positive the subject must be evaluated for the presence of HBV, HCV, or CMV by DNA (PCR) See Appendix D.
- Known histological transformation from CLL to an aggressive lymphoma (i.e. Richter's transformation / Hodgkin Lymphoma)
- 8. Evidence of ongoing systemic bacterial, fungal or viral infection, except localized fungal infection of skin or nails.
- Any severe and/or uncontrolled medical conditions or other conditions that could affect their participation in the study such as:
 - Symptomatic, or history of documented congestive heart failure (NY Heart Association functional classification III-IV) – See Appendix C
 - b. Myocardial infarction within 6 months of enrollment
 - c. OTcF >470 msec
 - d. Angina not well-controlled by medication
 - Poorly controlled or clinically significant atherosclerotic vascular disease including cerebrovascular accident (CVA), transient ischemic attack (TIA), angioplasty, cardiac/vascular stenting within 6 months of enrollment
- 10. Malignancy within 3 years of study enrollment except for adequately treated basal, squamous cell carcinoma or non-melanomatous skin cancer, carcinoma in situ of the cervix, superficial bladder cancer not treated with intravesical chemotherapy or BCG within 6 months, localized prostate cancer and PSA <1.0 mg/dL on 2 consecutive measurements at least 3 months apart with the most recent one being within 4 weeks of study entry.

- 11. Women who are pregnant or lactating.

This study is designed as a Phase 2, multicenter, single-arm trial to evaluate umbralisib in patients who discontinue a BTK or a PI3K-delta inhibitor due to intolerance. Approximately 55 patients, who have discontinued prior therapy with a BTK or PI3K-delta inhibitor due to intolerance, may be enrolled at approximately 20 sites in the US. Planned analysis will include approximately 50 evaluable patients assuming a 10% discontinuation rate.

Study Design

Enrollment

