2 OBJECTIVES AND ENDPOINTS

2.1 STUDY OBJECTIVES

PRIMARY OBJECTIVE

 To determine the progression free survival of umbralisib in patients who were intolerant to prior BTK and/or PI3K-delta inhibitors.

KEY SECONDARY OBJECTIVES

- To evaluate the overall response rate (CR + PR) and duration of response of umbralisib in patients who were intolerant to prior BTK and/or PI3K-delta inhibitors.
- To evaluate Time to Treatment Failure with umbralisib as compared to the prior kinase inhibitor therapy in patients with CLL.
- To evaluate the safety profile of umbralisib as compared to the safety profile of the prior kinase inhibitor therapy in patients with CLL.

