2.2 EFFICACY ENDPOINTS

Progression-free survival (PFS)

PFS is defined as the interval from Cycle 1/Day 1 to the earlier of the first documentation of definitive disease progression or death from any cause. Definitive disease progression based on standard criteria (Hallek et al. 2008) and occurring for any reason (i.e., increasing lymphadenopathy, organomegaly or bone marrow involvement; decreasing platelet count, hemoglobin, or neutrophil count; or worsening of disease-related symptoms) other than lymphocytosis.

Time to treatment failure (TTF)

TTF is defined as a composite endpoint measuring time from Cycle 1/Day 1 to discontinuation of treatment for any reason, including disease progression, treatment toxicity, and death.

Overall response rate (ORR)

ORR is defined as sum of CR and PR rates.

Duration of response (DOR)

DOR is defined as the interval from the first documentation of CR or PR to the earlier of the first documentation of definitive disease progression or death from any cause.

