⁶ Baseline CT scan within 30 days prior to Cycle 1/Day 1; then during cycles 3, 6, 9, 12 and at least every 6 cycles for 24 cycles, then every 12 cycles thereafter or more frequent if warranted (+/- 14 days). CT imaging should be performed at EOT visit if it hasn't been completed within past 30 days.

⁷ If discontinued due to reasons other than progression, follow up every 3 months on status of disease progression. Patients who discontinue from study

⁷ If discontinued due to reasons other than progression, follow up every 3 months on status of disease progression. Patients who discontinue from study treatment after cycle 12 (for reasons other than disease progression) should be followed for progression, approximately every 6 months for 24 months then every 12 months or more frequent if warranted.

⁸ Serum pregnancy test within 72 hours prior to starting treatment on Cycle 1 / Day 1.

⁹ Urine pregnancy test within 72 hours of Day 1 of each cycle. Administer test with each drug dispensation after Cycle 6.

¹⁰ Peripheral Blood (screening, Cycle 2/Day 1 and at disease progression) and buccal swab (screening only) samples for correlative analyses. See lab manual.

¹¹ Additional peripheral blood sample will be collected at screening only and analyzed at central lab for high-risk cytogenetics as well as BTK/PI3K resistance and activating mutations/deletions of prognostic value.

¹² Bone Marrow aspirate/ biopsy performed at baseline at the discretion of investigator to evaluate cytopenias. Bone marrow to be repeated if patient meets clinical criteria for CR to confirm this finding, as per iwCLL criteria.

¹³ Subjects who discontinue study drug should have a follow up visit or telephone call to assess for AEs. This should be done 30 days (+/- 7 days) after the last dose of study drug. In addition, SAEs will be reported for 30 days after the last dose of study drug.

Laboratory assessments will be collected as specified in the study assessments and treatment schema. Please refer to the study/lab manual for instructions outlining collection and shipment procedures for lab samples for central review.

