9.7 EFFICACY ANALYSES

Each subject will be assigned to one of the following categories: 1) complete response, 2) partial response, 3) stable disease, 4) progressive disease, 5) early death from malignant disease, 6) early death from toxicity, 7) early death because of other cause, or 8) unknown (not assessable, insufficient data).

Many of the efficacy measures will be based on disease assessments. The best clinical response as well as disease progression will be determined by the treating investigator. Scans should be kept on file in cases where independent review or confirmation may be warranted. Definitive disease progression will be based on standard criteria (Hallek et al. 2008, Appendix A – CLL Response Definition) occurring for any reason (e.g., increasing lymphadenopathy, organomegaly or bone marrow involvement; decreasing platelet count, hemoglobin, or neutrophil count; or worsening of disease-related symptoms) other than lymphocytosis.

Subjects will be treated until disease progression, unacceptable toxicity or the end of the study. Upon the end of the study, subjects without disease progression may be transitioned to an open label compassionate use study.

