9.8 MISSING VALUE HANDLING PROCEDURES

In general, other than for partial dates, missing data will not be imputed and will be treated as missing. The algorithms for imputation of partial dates may vary depending upon the parameter.

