9.9.2.2 TIME TO TREATMENT FAILURE

Time to Treatment Failure (TTF) is defined as a composite endpoint measuring time from Cycle 1/Day 1 to discontinuation of treatment for any reason, including disease progression, treatment toxicity, and death. Estimates of median TTF will be made using Kaplan-Meier methods.

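### The efficacy population requires an undefined minimum of assessment, so unassessed early deaths can leave PFS and unassessed early exits can leave ORR and TTF, in the drug's favour

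*Combined protocol and SAP*

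**What the plan says.** Section 9.3 defines two populations. The safety set is everyone who takes a dose. The set labelled ITT is narrower: "The ITT population will include all enrolled subjects who provide some efficacy assessments", and all efficacy analyses use it. No section defines an efficacy assessment for this purpose.

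The endpoint definitions need no such assessment:

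- **PFS** (Sections 2.2 and 9.9.1) runs from Cycle 1/Day 1 to the earlier of the "first documentation of definitive disease progression or death from any cause".
- **TTF** (Section 9.9.2.2) runs from Cycle 1/Day 1 to "discontinuation of treatment for any reason, including disease progression, treatment toxicity, and death".
- **ORR** (Section 9.9.2.1) is a percentage of subjects with CR or PR. No denominator is named.

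Two other sections bear on the point. Section 9.7 says "Each subject will be assigned to one of the following categories", and its list includes three kinds of early death and a category for subjects who cannot be assessed. Section 9.8 says that, in general and apart from partial dates, "missing data will not be imputed and will be treated as missing".

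The synopsis plans 55 enrolled: "Planned analysis will include approximately 50 evaluable patients assuming a 10% discontinuation rate". It does not say who the other five are.

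**The concern.** A set whose membership can depend on post-enrolment data is not intention-to-treat, whatever its label. Here it can remove outcomes that the endpoint definitions count as failures.

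- **PFS:** a treated subject who dies before any assessment has an event by definition but may fall outside the set.
- **ORR:** an early exit without a response assessment may leave the denominator. With missing data left as missing, no rule makes that subject a non-responder.
- **TTF:** an early toxicity stop without an assessment is a treatment failure but may not be counted.

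Two groups are not part of the concern. Event-free withdrawals do not bias PFS, and a documented progression is itself an assessment.

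With one arm and a fixed null, no control group shares the exclusion. TTF also serves a key secondary objective in Section 2.1, "To evaluate Time to Treatment Failure with umbralisib as compared to the prior kinase inhibitor therapy", so losing early stops on umbralisib would tilt that comparison too.

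**Working it through.** **Inputs from the synopsis (Statistics).** 55 enrolled, about 50 analysed (55 × 0.9 = 49.5); null median 8 months, alternative 12; one-sided one-sample log-rank test at 5%; 12 months of accrual, 24 months of follow-up; stated power 82%. Exponential times and uniform accrual are assumed.

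**The plan's own figure.** With n = 50 and a true median of 12 months, the event probability is 1 − (2⁻² − 2⁻³)/ln 2 = 0.820, so about 41.0 events are expected.

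- Log-hazard formula: Φ(√41.0 × ln 1.5 − 1.645) = Φ(0.95) = 82.9%.
- Exact variance under the alternative: 81.6%.

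The stated 82% reproduces for 50 subjects.

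**PFS under the null.** The statistic is Z = (O − E)/√E, with null hazard ln 2/8 = 0.0866 per month; reject if Z < −1.645.

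- An unassessed withdrawal censored at Cycle 1/Day 1 adds 0 to O and 0 to E. Removing it changes nothing.
- A death at month 1, as an example, adds 1 to O and 0.087 to E. Removing it moves O − E by about −0.91. With E about 50.7 for 55 subjects, Z moves by about −0.91/√50.7 = −0.13 per death, towards rejection.

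The simulation used 55 enrolled, a true median of 8 months and 200,000 replicates. In each replicate exactly k subjects with an event before 2.5 months, standing for unassessed deaths, were removed. The documents do not give k. The last column is −8 × log₂[0.5 × (1 − k/55)].

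| k removed | False-positive rate, variance E | Variance (O+E)/2 | Apparent median (months) |
|---|---|---|---|
| 0 | 4.2% | 5.1% | 8.0 |
| 1 | 5.4% | 6.5% | 8.2 |
| 2 | 7.0% | 8.3% | 8.4 |
| 3 | 8.8% | 10.3% | 8.6 |

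The plan does not name the variance. The second form is shown because it brings the rate without exclusions close to the nominal 5%. With exactly 24 months of follow-up per subject and variance E, the rates are 4.2%, 5.5%, 7.1% and 9.1%.

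**ORR.** Assume 25 responders, with every excluded subject a non-responder (exact intervals):

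- none excluded: 25/55 = 45.5% (95% CI 32.0 to 59.4)
- one excluded: 25/54 = 46.3%
- five excluded: 25/50 = 50.0% (35.5 to 64.5)

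**TTF.** Assume a true median of 8 months. By the same median formula, removing 1, 3 or 5 early stops makes it read 8.2, 8.6 or 9.1 months.

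**Power if all 55 are kept.** Simulated power at a true median of 12 months (100,000 replicates, variance E) is 83.3% with 50 and 86.6% with 55. The exact-variance formula gives 84.6% with 55.

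**The case against.** The strongest reply is that the harm needs a narrow reading. The rule asks only for some assessment. A baseline CT is scheduled for everyone, and examination and blood counts are scheduled at screening and on Days 1, 8 and 15 of Cycle 1. Blood counts are response criteria in Sections 8.5 and 8.6. On that reading nearly every dosed subject qualifies. Those who stop are also covered: footnote 6 of the Section 5 schedule says "CT imaging should be performed at EOT visit" if there is no scan within the past 30 days, and Sections 4.4, 6.3 and 6.5 continue follow-up for progression. This stands as a limit on size. It does not settle which reading applies, and in an open-label trial that choice could be made after outcomes are known.

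The scenarios can also be called severe. About 55 × (1 − 2^(−2.5/8)) = 10.7 events fall before 2.5 months under the null, so k = 3 treats 28% of them as unassessed deaths. If the number removed is random with mean 0.5, the false-positive rate is 4.7% with variance E (5.7% with the other form); with mean 1 it is 5.3% with variance E. That is fair: small exclusion rates do little harm. Five exclusions is an upper illustration, because the planned 10% is not broken down by cause.

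Section 9.7 may be read as keeping unassessed subjects in the response table. That softens the ORR part, but it neither sets the denominator nor overrides Section 9.3, and it does not address PFS or TTF.

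On TTF, Section 9.9.2.2 plans only a Kaplan-Meier median, and all subjects had stopped the prior inhibitor, so the comparison is already selected. The comparison is nevertheless a stated objective.

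Finally, a one-dose rule drops subjects enrolled through the IWRS but never dosed. PFS and TTF start at Cycle 1/Day 1, so no information on either is lost.

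**Conclusion.** The concern holds. Section 9.3 sets a rule for all efficacy analyses that can remove failures counted by the endpoint definitions, and any resulting bias favours umbralisib. Exclusion is possible, not certain. The bias is close to nil if baseline or Cycle 1 data qualify. If one to three unassessed early deaths were lost, the nominal 5% test would run at about 5.4% to 8.8%, or 6.5% to 10.3% with the alternative variance, and a true 8-month median would read 8.2 to 8.6 months. These figures rest on exponential times and an assumed number of exclusions. The 82% power figure is not in dispute. The wording should be corrected before the analysis.

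**What to change.** In Section 9.3, define the primary efficacy population as all subjects who take at least one dose of umbralisib, and state for each endpoint:

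- **PFS:** a death without any assessment is an event; other subjects with no post-baseline assessment are censored at Cycle 1/Day 1.
- **ORR:** every treated subject stays in the denominator, and no post-baseline response assessment counts as non-response. State this as an exception to Section 9.8.
- **TTF:** every treated subject is counted.

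Keep a response-evaluable set as supportive only, with efficacy assessment defined as post-baseline. Align the synopsis and Sections 9.3, 9.7 and 9.8, including what the 50 evaluable subjects are.

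The cost is protocol and SAP wording. The estimates may read slightly lower than under the present rule. Planned power does not fall, as the comparison of 50 with 55 subjects shows.
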